# **A NOVEL TECHNIQUE FOR THYROPLASTY TYPE 1, WITH PROLENE MESH IMPLANT.**

**NCT04458818**

**Date: 3 Mar 2021**

**Objective:** To evaluate a new approach of vocal cord medialization using prolene mesh as an implant material for thyroplasty type 1.

**Study Design:** Interventional, prospective study.

**Place and Duration of study:** Ent unit of a tertiary care hospital in Pakistan from May 2020 to January 30 2021.

**Materials and Methods:** Patients of age 15 years onwards and with vocal cord paralysis/paresis due to multiple causes were included in the study. Patients with neoplasm, trauma and underlying muscular dystrophy were excluded. All patients were counselled properly and given the choice of intervention by prolene mesh implant. Consenting patients were subjected to routine blood investigations with fiber optic laryngoscopy and imaging with Computerized Tomography scan (where applicable). Procedure was performed under local anesthesia with mild sedation, so that the patient will remain vocally responsive for the assessment of voice and breathing intraoperatively. Pre and postoperative voices were recorded with a standard microphone at 15cm distance from the mouth in a quiet room. Maximum phonation time (MPT) while vocalizing the vowel sound 'eee' and Maximum words count (MWC) in a single breath (counting numbers) were recorded pre and post operatively. Maximum three attempts were allowed to each patient and the better score of the three was recorded in the data. For subjective assessment of voice quality Visual (1-10) analogue score (VAS) was used both pre and postoperatively.

Hospital ethical committee's approval was taken and clinical trial registration was obtained from [clinicaltrials.org](https://clinicaltrials.org). The surgery will be performed under local anesthesia (lignocaine with adrenaline 2%) and procedural sedation with propofol 25-100mcg/kg/min (only sedative dose) will be administered, so that the patient remains vocally responsive during the procedure. Incision will be made at the lower border of thyroid cartilage under aseptic measures. Skin flaps will be raised in sub-platysmal plane, strap muscles will be separated in the midline to expose the laryngeal cartilaginous framework. A simple laryngeal window approach will be used to place the Ethicon prolene mesh 6 x 6cm Swiss roll, secured with prolene 2/0 suture trimmed to the required size. Post op voice analysis will be done on 7th day and 14th post-operative day. Monthly follow up will be advised after that.

The results will be analyzed using IBM SPSS Statistics version 20. Variables defined would be compared between the pre-operative and postoperative groups. For normal data paired sample t-test would be used and for abnormally distributed data non parametric t-test would be used. P-value of less than 0.05 will be taken as significant.

**Results:** In this study, 39 patients satisfied the inclusion criteria. There were 23 females (38.5%) and 15 male (61.50%) patients. 26 patients (66.67%) had unilateral Vocal Cord

dysfunction while 13 (33.33%) had bilateral dysfunction. 46.15% (n=18) of these were post thyroidectomy, 20.51% (n=8) patients had idiopathic vocal cord paralysis and 33.33% (n=13) had miscellaneous causes. The median time passed since development of disease to the time of surgery was 6 months with a range of 2 months to 120 months.

The categorical data analysis was done with paired sample t-test, which indicated an improvement in Visual analogue (1-10) score of voice quality post operatively from 4.77 to 7.64 (p value <0.001). MWC increased from 11.33 to 18.28 (p value <0.001). The median increase in MPT in our study was about 5 seconds (n=39) (p value <0.001). For male patients median MPT increase was 7 seconds (n=15) and for females 4.5 seconds (n=24). These parameters indicated significant benefit to the patient and improvement in the quality of life.

There were no major complications observed in our study except for one instance of skin infection and hematoma. There were no graft displacements, extrusions and airway obstruction in our study. Four of our patients suffered temporary voice change due to upper respiratory tract infection which recovered in a span 5 days.

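### The conclusion of patient benefit and better quality of life goes beyond an uncontrolled before-after comparison in which no quality-of-life measure is described

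*Combined protocol and SAP*

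**What the plan says.** Study Design gives an interventional, prospective study and mentions no comparison group. Under Materials and Methods, every patient was counselled and offered the mesh implant, so treatment was open. The analysis paragraph compares variables only between the pre-operative and post-operative states, at a 0.05 level.

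Three outcomes are measured. MPT and MWC are taken as the best of up to three attempts. The third is the voice-quality score, and its whole method is one sentence: "For subjective assessment of voice quality Visual (1-10) analogue score (VAS) was used both pre and postoperatively". The rater, the rater's knowledge of the time point and the scoring order are not given. Voices were also recorded under standard conditions ("Pre and postoperative voices were recorded with a standard microphone at 15cm distance from the mouth in a quiet room"), but the recordings are not linked to the VAS. Post-operative voice analysis is set for days 7 and 14, with monthly follow-up advised afterwards.

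Results reports a VAS "score of voice quality post operatively from 4.77 to 7.64 (p value <0.001"), an MWC rise from 11.33 to 18.28 with p<0.001, and for MPT: "The median increase in MPT in our study was about 5 seconds (n=39) (p value <0.001"). It does not say which visit gave the post-operative VAS mean. It then concludes: "These parameters indicated significant benefit to the patient and improvement in the quality of life".

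**The concern.** The concluding sentence makes two claims that the design cannot carry.

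The first is benefit from the procedure. In one openly treated group, a before-after difference contains the implant's effect together with anything else that changed between the two assessments. For a subjective score the main rival is expectation. For MWC and MPT it is effort or practice, since both depend on how hard and how often the patient tries. For all three it is recovery over time: the interval from onset to surgery had a median of 6 months but started at 2 months.

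The second is quality of life. None of the three outcomes is described as a quality-of-life measure, and no such instrument appears in the document.

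A reader could therefore take the full 2.87 points as the implant's effect on voice quality and believe that quality of life was assessed. The unstated rater and visit make the score harder still to interpret. Results also mentions four patients with temporary voice change from respiratory infection, without dates, so it is unclear whether this touched the scores used.

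**Working it through.** **Inputs from Results:** VAS means 4.77 and 7.64; n = 39; p<0.001; MWC 11.33 and 18.28; median MPT gain about 5 seconds. **Not given:** the SD, SE or confidence interval of the VAS change. **Assumed:** a two-sided paired t-test, 39 VAS pairs, and a range of SDs.

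**1. Size of the VAS change.** 7.64 − 4.77 = 2.87 points. This is 2.87/4.77 = 60% of baseline, or 2.87/9 = 32% of the width of a 1-10 scale.

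**2. Is p<0.001 plausible?** It cannot be reproduced exactly without an SD, but it can be bounded. With 38 degrees of freedom, two-sided p = 0.001 corresponds to t = 3.566.

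- Largest SE: 2.87/3.566 = 0.805.
- Largest SD of change: 0.805 × √39 = 0.805 × 6.245 = 5.03.

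The reported p-value holds for any SD of change up to about 5. The 95% interval is 2.87 ± 2.024 × SD/6.245:

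| Assumed SD of change | Half-width | 95% CI for the change |
|---|---|---|
| 1.5 | 0.49 | 2.38 to 3.36 |
| 2 | 0.65 | 2.22 to 3.52 |
| 3 | 0.97 | 1.90 to 3.84 |
| 4 | 1.30 | 1.57 to 4.17 |

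Sampling error alone is an unlikely explanation of the change.

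**3. What the p-value tests.** The observed mean change can be written as

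change = implant effect + expectation + effort or practice + recovery over time.

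The paired test asks whether this sum is zero. With one group there is one observed sum per outcome and no second equation to isolate the first term. A smaller p-value or narrower interval describes the sum more precisely but does not divide it.

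**4. The conclusion set against what was measured.**

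| Element of the conclusion | What supports it | What is absent |
|---|---|---|
| Improvement after surgery | VAS +2.87; MWC 18.28 − 11.33 = +6.95; MPT about +5 s | Nothing needed beyond these |
| Benefit due to the implant | The same three changes | Any comparator |
| Better voice quality | VAS only; MWC and MPT measure count and duration | Rater, masking, visit |
| Better quality of life | None | Any quality-of-life measure |

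**The case against.** The strongest reply is that MWC and MPT are counted or timed, are less open to rating bias than the VAS, and moved the same way. That stands as support for a real change in vocal function. It does not settle attribution, because both are effort-dependent, best of up to three attempts and uncontrolled. Nor do they measure how the voice sounds, so they cannot confirm the 2.87 points.

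A second reply is that patients cannot be masked to this surgery, and that if the VAS was self-rated, lack of masking is inherent in the outcome. This also stands. The point is the claim made from the data, not a failure to mask patients or add an arm.

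A reader might infer more than the documents support:

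- **That the VAS gain is spurious or its significance unsafe.** Step 2 shows otherwise, and nothing in the documents says how large any bias is. A percentage reduction would only restate whatever bias was assumed.
- **That a VAS pair is missing.** Results says "There were 23 females (38.5%) and 15 male (61.50%) patients", which sums to 38. The MPT split later in Results is 15 males and 24 females, or 39. The percentages fit 39 with labels exchanged (15/39 = 38.5%, 24/39 = 61.5%). Laterality (26 + 13) and cause (18 + 8 + 13) also sum to 39. If scores are whole numbers, 186/39 = 4.77 and 298/39 = 7.64, whereas 38 gives 4.76 or 4.79 and 7.63 or 7.66. The count of 23 looks like a slip.
- **That the VAS was scored by someone present at surgery.** Materials and Methods says "the patient will remain vocally responsive for the assessment of voice and breathing intraoperatively", but does not connect that assessment with the VAS.

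**Conclusion.** The concluding sentence is wrong as written. The data support an improvement from before to after surgery in three voice measures. They do not support a quality-of-life conclusion, and they do not show how much of the improvement is due to the implant.

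The sizes in question are the full 2.87 VAS points, the 6.95-word MWC gain and the roughly 5-second MPT gain. The share of each that is due to the implant cannot be estimated from the documents. That significance is secure rests on assuming 39 VAS pairs, a two-sided paired test and an SD of change below about 5.

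The unstated VAS rater, masking status and visit are missing detail. They do not show that the rating was biased.

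**What to change.** **Required, at the cost of wording only.**

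- Restate the conclusion as an uncontrolled before-after improvement in VAS (4.77 to 7.64), MWC and MPT in one treated group.
- Remove the quality-of-life claim.
- Label the VAS as a subjective rating with no masking described. State who scored it and which post-operative visit (day 7, day 14 or later) produced 7.64.
- Give the SD and 95% confidence interval of the paired VAS change, which the existing data should supply.

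**Optional supplement.** If the recordings were kept and suit a voice-quality rating, they could be scored in random order with time-point labels removed. The result should be reported as post hoc, beside the VAS and not in its place. With one recording before and one after per patient, that is 39 × 2 = 78 clips, or 88 with about 10 repeats for consistency. It takes staff time but no new visit or procedure.

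Its limits should be stated. Retention and content of the recordings are not documented, results are already known, masking may fail where the change is obvious, and a single rater gives limited reliability. Rescoring addresses rating bias, not attribution to the implant. If the VAS was self-rated, it measures a different construct and cannot correct the 2.87.

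### Does leaving the post-operative visit unnamed (day 7 or day 14), with no spread given for any change, undermine the paired comparison?

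*Combined protocol and SAP*

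**What the plan says.** The combined protocol and SAP fixes two assessment days in the paragraph on surgery and follow-up: "Post op voice analysis will be done on 7 th day and 14 th post-operative day". After that, "Monthly follow up will be advised after that", with no voice measurement attached. The statistical paragraph then reads "Variables defined would be compared between the pre-operative and postoperative groups", and its test rule is "For normal data paired sample t-test would be used and for abnormally distributed data non parametric t-test would be used". Neither sentence names a day or says how two visits would be combined.

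Materials and Methods says only that the measures were taken before and after surgery. For MPT and MWC it adds a scoring rule: "Maximum three attempts were allowed to each patient and the better score of the three was recorded in the data". VAS has no such rule.

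The Results report VAS rising from 4.77 to 7.64, MWC from 11.33 to 18.28, and a median MPT gain of about 5 seconds in 39 patients, each with p<0.001. No day and no measure of spread accompanies any of them.

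**The concern.** A paired test needs one post-operative value per patient, and the plan collects two. The text would fit day 7, day 14, their mean or the better of the two, and the reader cannot tell which. The first three are harmless. The last is not: it would set the best of up to six attempts after surgery against the best of up to three before, which favours improvement even if surgery did nothing. Because the scoring rule already keeps a best value, the worry is not absurd.

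Two further points sharpen it. The complications paragraph notes "Four of our patients suffered temporary voice change due to upper respiratory tract infection which recovered in a span 5 days"; an episode shorter than the seven days between visits could touch one visit and spare the other. And without an SD, IQR or interval, the reader of a single-arm study of 39 patients sees that the changes are significant but not how precisely they are known. At stake are the timing of the gain, its precision and, under the worst reading, the p-values.

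**Working it through.** The documents contain no sample size or power figure to reproduce. The reported p-values cannot be reproduced either, since no SD or test statistic is given. Three checks are still possible.

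**1. Does the choice of visit damage the test?** Simulation with no true change, n=39, paired t-test, attempts normal with SD 1, and between-session SD assumed at 0, 0.5 or 1:

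| Post-operative value used | P(p<0.05) | P(p<0.001) |
|---|---|---|
| One visit | 4.9-5.0% | 0.1% |
| Mean of both visits | 4.8-5.1% | 0.1% |
| Visit with the smaller p | 8.8-9.0% | 0.2% |
| Better of both visits, per patient | 73.5-74.9% | 20.9-21.9% |

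Only the last row is seriously wrong. Set it beside the scoring rule in Materials and Methods, which allows at most three attempts and keeps the best of the three. That selects among attempts, not between days, and a best of six exceeds the stated maximum. VAS has no best-of rule at all.

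Even testing both days and reporting the more favourable one gives p<0.001 in only 0.2% of null trials, and all three reported results are below 0.001. Three outcomes at two visits make six tests. Bonferroni then asks for 0.05/6 = 0.0083, which single-visit results with p<0.001 meet.

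**2. What does p<0.001 already imply about precision?** Inputs from the Results: n=39 (38 df), VAS gain 7.64 - 4.77 = 2.87, MWC gain 18.28 - 11.33 = 6.95. Assume a two-sided paired t-test.

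- p<0.001 requires gain/SE > 3.566, so SE < gain/3.566.
- The 95% half-width is 2.024 x SE, hence below (2.024/3.566) x gain = 0.568 x gain.
- VAS: 0.568 x 2.87 = 1.63, so the interval is no wider than 1.24 to 4.50. The SD of change is at most (2.87/3.566) x √39 = 5.03.
- MWC: 0.568 x 6.95 = 3.95, so no wider than 3.00 to 10.90. The SD of change is at most (6.95/3.566) x √39 = 12.17.
- If the p-values were one-sided, the critical value is 3.319 and the limits become 1.12 to 4.62 and 2.71 to 11.19.

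These are ceilings. For VAS, suppose pre and post scores were spread uniformly over 1 to 10 and uncorrelated. Each SD is 9/√12 = 2.6, the SD of change is 2.6 x √2 = 3.7, and the half-width is 2.024 x 3.7/√39 = 1.2, giving about 1.7 to 4.1.

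For MPT only a median is given and its test is not named, so no interval in seconds follows.

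**3. Do the figures reveal the visit?** The four reported means match whole-number totals over 39 patients: 186/39 = 4.77, 298/39 = 7.64, 442/39 = 11.33, 713/39 = 18.28. If scores are whole numbers, this fits one post-operative value for each of the 39. It fits a mean of two visits equally well (596/78 = 7.64, 1426/78 = 18.28). It does not identify the day.

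The four temporary voice changes add nothing that can be computed. Their timing is not given; they may have fallen between visits or in the later monthly follow-up.

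**The case for a change.** The strongest opposing argument is that this gap differs from a loosely named test. A reader can guess that the non-parametric option means a paired rank test, but cannot work out which day a VAS of 7.64 belongs to. The scoring rule does not say in so many words that three attempts means three per session. If the better visit had been taken, the MPT bias would be 0.42, 0.51 or 0.70 attempt-SDs at session SD 0, 0.5 or 1. It would account for the whole 5 seconds at an attempt SD of 5/0.42, about 12 seconds, in the first case and 5/0.70, about 7 seconds, in the last. Reporting both days with intervals appears cheap.

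What stands is that the visit and the spread are missing and that nothing else in the documents supplies them. What does not stand is the step from silence to bias, because no text says or suggests that visits were combined. The remedy is also less certain than it looks. Only the best score was recorded, so attempt numbers may not be recoverable, and the documents do not show that separate day 7 and day 14 values exist for every patient. The study period ended on 30 January 2021 and the document is dated 3 March 2021 with results in it, so a visit chosen now would be post hoc.

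**Conclusion.** No change to the plan follows. This is missing detail that an analyst fills sensibly: use one scheduled visit, or the mean of both, in a paired test. Each choice keeps the error rate at about 5%. The 73-75% figure belongs to a scoring rule that the documents do not contain.

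The direction of the VAS and MWC results is secure if they came from a paired t-test on single-visit or averaged values. Their 95% intervals exclude zero, at 1.24 to 4.50 and 3.00 to 10.90 at the widest (two-sided). For MPT, the size of the uncertainty cannot be judged from the text.

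A full report would do well to name the visit and the test behind each figure and to give spread or intervals. That is a clarification of reporting; it does not correct the analysis.

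### Do the mismatched sex counts and percentages in the Results call for a change to the plan?

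*Combined protocol and SAP*

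**What the plan says.** All the relevant figures are in the Results section of the combined protocol and SAP.

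- Total: "In this study, 39 patients satisfied the inclusion criteria".
- Sex: "There were 23 females (38.5%) and 15 male (61.50%) patients".
- Laterality: 26 unilateral (66.67%), and the sentence continues "dysfunction while 13 (33.33%) had bilateral dysfunction".
- Cause: "46.15% (n=18) of these were post thyroidectomy, 20.51% (n=8) patients had idiopathic vocal cord paralysis and 33.33% (n=13) had miscellaneous causes".
- MPT overall: "The median increase in MPT in our study was about 5 seconds (n=39".
- MPT by sex: "For male patients median MPT increase was 7 seconds (n=15) and for females 4.5 seconds (n=24".

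The analysis paragraph just before the Results compares pre-operative with postoperative values, using a paired t-test or a nonparametric counterpart. It names no sex comparison, stratification or adjustment. The document mentions no patient of unknown sex, no exclusion after enrolment and no dropout.

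**The concern.** The sex sentence contradicts itself and its surroundings in two ways. Its counts fall one short of the stated total and disagree with the female denominator used for MPT. Its percentages make males the majority while its counts make females the majority.

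Two consequences would matter if they were real. First, a count of 38 could mean that one patient is absent from some results. Second, sex is the only subgroup with its own efficacy figure (7 seconds for males, 4.5 for females). If the sex coding were reversed, those two medians would carry the wrong labels.

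**Working it through.** **Inputs.** From the Results: N = 39; baseline sex counts 23 and 15; printed percentages 38.5 (female) and 61.50 (male); MPT denominators 15 male and 24 female.

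**1. Sums of counts.**
- Baseline sentence: 23 + 15 = 38, which is 39 − 1.
- MPT sentence: 15 + 24 = 39.
- The male count is 15 in both sentences, so the conflict is confined to the female count, 23 against 24.

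**2. Percentages, 100 × count / base.**

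| Count | Base 39 | Base 38 |
|---|---|---|
| 15 | 38.46% | 39.47% |
| 23 | 58.97% | 60.53% |
| 24 | 61.54% | 63.16% |

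The printed figures do not reproduce as labelled on either base. On 39, 38.5% arises only from a count of 15 and 61.5% only from 24. On 38, no whole count gives either: 14/38 = 36.84% and 15/38 = 39.47% lie on either side of 38.5%, and 23/38 and 24/38 lie on either side of 61.5%. The percentages were therefore calculated from a 24/15 split of 39 patients, and the 23 did not enter them. The gap between the two is 61.54 − 38.46 = 23.08 points, far beyond rounding.

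**3. Neighbouring breakdowns on base 39.**
- Laterality: 26/39 = 66.67%, 13/39 = 33.33%; 26 + 13 = 39.
- Cause: 18/39 = 46.15%, 8/39 = 20.51%, 13/39 = 33.33%; 18 + 8 + 13 = 39.

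All five reproduce. Among the patient characteristics, only the sex sentence fails.

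**4. Is a patient missing from an outcome?** Overall MPT is printed with n = 39. The voice score and word count carry no n, but their means can be tested. Assume that individual scores are whole numbers, which is natural for a word count and likely for a 1–10 score. A mean on 39 patients must then be a whole total divided by 39.

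| Printed mean | On 39 | Nearest on 38 |
|---|---|---|
| 4.77 | 186/39 = 4.769 | 181/38 = 4.763, 182/38 = 4.789 |
| 7.64 | 298/39 = 7.641 | 290/38 = 7.632, 291/38 = 7.658 |
| 11.33 | 442/39 = 11.333 | 430/38 = 11.316, 431/38 = 11.342 |
| 18.28 | 713/39 = 18.282 | 694/38 = 18.263, 695/38 = 18.289 |

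All four round correctly on 39 and none does on 38. Under that assumption, no patient is missing from these results.

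**5. Are the MPT labels reversed?** The alternative is 15 females and 24 males, with the percentages correctly placed. That needs the sexes to be swapped in both the baseline counts and the MPT sentence, and the count of 23 would still be wrong. The reading with 24 females needs one wrong digit and one transposition, both in a single sentence. If MPT was recorded in whole seconds (the document does not say), a median of 4.5 also requires an even group size. That fits 24 and rules out 15 or 23.

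**The case for a change.** The case for acting is that the sentence is wrong on its face and no base or rounding rescues it. One correction alone does not mend it either. Changing 23 to 24 leaves the percentages reversed, and exchanging the percentages leaves 23/39 = 59.0% where 61.5% is printed. A reader who sees only the baseline sentence cannot tell which sex was in the majority, and the sex-specific medians make that a fair question. Putting it right costs one frequency table and a look at the sex coding.

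The arithmetic stands in full. A misread digit when the PDF was converted to text could explain 23 for 24, but not the exchanged percentages. The objection fails on consequence. The MPT sentence already prints group sizes that are consistent with each other and total 39, so an attentive reader can resolve the conflict from the same section. The sex medians are descriptive, with no p-value and no hypothesis attached. No conflict is shown in their labels, so checking the coding is a precaution.

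**Conclusion.** The discrepancy is real and clerical, and it gives no reason to change the plan. Its size is one patient in the female count (23 against 24) and two percentages placed against the opposite sexes. The coherent reading is 24 females (61.5%) and 15 males (38.5%). This is an inference from the printed denominators and percentages, to be confirmed in the source data if the sentence is tidied in a later report.

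The overall changes in voice score, word count and MPT are within-patient comparisons, so how the sexes are tallied cannot alter them. Even in the unlikely event of swapped labels, only the two descriptive MPT medians would change places. The conclusion assumes that the 39 patients are the analysed set. The document states this for MPT, and the means support it for the other two measures if scores are whole numbers.

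### The Results conclude patient benefit and better quality of life from an uncontrolled pre/post change in three voice measures, with no quality-of-life data reported

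*Combined protocol and SAP*

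**What the plan says.** Materials and Methods describes three efficacy measures. MPT and MWC are performance tasks, with the best of up to three attempts kept; for the second, "Maximum words count (MWC) in a single breath (counting numbers) were recorded pre and post operatively". The third is a rating: "For subjective assessment of voice quality Visual (1-10) analogue score (VAS) was used both pre and postoperatively". The text does not say who gave the rating.

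The statistical paragraph before the Results sets the comparison: "Variables defined would be compared between the pre-operative and postoperative groups". The test for normally distributed data is paired, so these groups are two time points in the same patients. No comparator, randomisation or blinding is described anywhere. Study Design says only that the study is interventional and prospective.

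The Results give three findings:

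- VAS: the test "indicated an improvement in Visual analogue (1-10) score of voice quality post operatively from 4.77 to 7.64 (p value <0.001").
- MWC: "MWC increased from 11.33 to 18.28 (p value <0.001").
- MPT: "The median increase in MPT in our study was about 5 seconds (n=39) (p value <0.001").

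After a breakdown of MPT by sex comes the concluding sentence: "These parameters indicated significant benefit to the patient and improvement in the quality of life".

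**The concern.** The concluding sentence makes two claims, and both go beyond the findings that precede it.

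The first is improved quality of life. The phrase occurs only in this sentence. The Methods list no quality-of-life or voice-handicap questionnaire, and the Results give no such score. A reader would take as a trial finding something that was inferred from voice measures.

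The second is significant benefit to the patient. The p-values test whether the measures changed between two occasions. They do not separate the effect of the implant from anything else that changed between those occasions. The document gives no threshold for a worthwhile change on any of the three measures, so statistical significance does not amount to a stated level of benefit either.

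This is the sentence most likely to be quoted from the study, and it carries no qualification.

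**Working it through.** **1. What was measured against what was concluded**

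| Item | In the document | What it can support |
|---|---|---|
| MPT | Phonation task, best of up to three attempts | Change in phonation performance |
| MWC | Single-breath counting task, best of up to three attempts | Change in phonation performance |
| VAS, 1-10 | Subjective rating of voice quality, rater not stated | Change in rated voice quality |
| Quality of life | Concluding sentence only; no instrument, no score | Nothing can be computed |
| Control group | None described | No contrast with and without the implant |

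**2. Size of the reported changes** (inputs from the Results)

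- VAS: 7.64 - 4.77 = 2.87 points; 2.87/4.77 = 60.2%.
- MWC: 18.28 - 11.33 = 6.95; 6.95/11.33 = 61.3%.
- MPT: median increase about 5 seconds, n=39.

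**3. What the p-values establish**

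They cannot be reproduced, because no standard deviation, confidence interval or patient-level data are given. Their content can be bounded for VAS and MWC. Assume that the printed values are means (the text does not label them), that n=39 applies to both, and that the paired t-test was two-sided (sidedness is not stated).

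- The critical value for p=0.001 with 38 degrees of freedom is 3.566.
- The smallest standardised paired change giving p<0.001 is 3.566/√39 = 0.571.
- The largest standard deviation of the change compatible with p<0.001 is the mean change divided by 0.571. That is about 5.03 points for VAS and 12.17 for MWC.

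The reported p-values are therefore unsurprising for changes of this size. They support a real difference between the two occasions and say nothing about its cause. MPT is left out of this calculation because it is summarised as a median.

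**4. Why the cause stays open**

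- Time since onset had a median of 6 months and a range of 2 to 120. With 39 patients the median is the 20th ordered value, so at least 20 patients had had the condition for 6 months or less (assuming that all 39 durations were recorded). No requirement for a stable baseline is described, so recovery unrelated to the implant is not excluded.
- MPT and MWC depend on effort and practice. Allowing up to three attempts on each occasion does not remove a practice effect between occasions.
- The VAS is subjective and no blinding is described, so expectation is not excluded.

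The document gives no estimate of such non-specific change. For illustration only, if it were 0, 1 or 2 VAS points (an assumption), then 2.87 - 0 = 2.87, 2.87 - 1 = 1.87 or 2.87 - 2 = 0.87 points would remain for the implant. The data cannot choose among these values.

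**The case against.** The best defence is that nothing is hidden. Pre- and post-operative measurement is stated in the Methods, the comparison is paired, and no comparator is implied. Significance is defined in advance as p<0.05, and all three measures are reported at p<0.001. The concluding sentence follows directly on the three results and is worded as an inference from them. A better voice may well mean a better life.

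Much of this stands. The design is disclosed, and the pre/post improvements are not in dispute. What does not stand is the step from a disclosed pre/post change to benefit and quality of life presented as findings. That a better voice improves quality of life is plausible, but no reported data test it.

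Some stronger readings are tempting and are not supported:

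- **That quality of life was never assessed.** A reader might infer this. The document shows only that no instrument is named and no score is reported. It is a short, abstract-style text, and only the sponsor can say whether an instrument was used.
- **That labelling the comparison uncontrolled would allow the change to be credited to the implant.** It would not. The label describes the limitation and does not remove it.
- **That the scores were distorted by the four temporary voice changes** (4/39 = 10.3%). These are undated and recovered within 5 days. Nothing links them to a scored visit.
- **That the implant did not work.** The lack of a control leaves the cause undetermined; it does not show absence of effect.

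**Conclusion.** The point holds as a claim about the concluding sentence. The reported data support a statistically significant within-patient change in three voice measures: +2.87 VAS points, +6.95 MWC and a median of about 5 seconds in MPT. They support no statement about quality of life, because the document contains no quality-of-life result. They also leave undetermined the share of the change that is due to the implant.

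The textual part needs no assumption beyond reading the whole document. The bounds on the standard deviation rest on the assumptions stated with them, and the conclusion does not depend on those bounds. The denominator of 39 is taken from the Results, where the MPT breakdown gives 15 + 24 = 39. The same section also prints 23 females with 15 males, which sums to 38; that inconsistency needs correcting but does not affect this point.

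This is a fault of interpretation. On what the document shows, no test or dataset has to change. It should be fixed because it alters what the trial is said to have found.

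**What to change.** Replace the concluding sentence.

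1. Delete the quality-of-life clause. If an instrument was used, name it and report its pre- and post-operative data instead.
2. Replace the benefit clause with what was observed, for example: *In an uncontrolled comparison within the same patients, voice-quality VAS rose from 4.77 to 7.64, MWC from 11.33 to 18.28 and MPT by a median of about 5 seconds (each p<0.001).*

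This costs one sentence and needs no new data, unless the sponsor chooses to report a quality-of-life instrument. The price is a less favourable conclusion, which is the one the data support.

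Minor reporting note: the schedule says "Post op voice analysis will be done on 7 th day and 14 th post-operative day", with monthly follow-up advised afterwards, yet the Results give one post-operative value or change per measure. State which visit the values come from. If they come from one visit, this takes a few words. If visits were combined, a small re-analysis by visit would be needed; the document does not show which case applies.
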